3 STUDY DESIGN

Figure C: Study Design

At baseline (week 0), all patients will do a one-week sleep actigraphy and complete SDSC questionnaire. At week 1, patients will be randomised to one of the 4 treatment regimen that is determined by the first period of the sequence they are assigned to. Re-evaluation with sleep actigraphy and SDSC questionnaire will be done at week 4, 6 and 10. At week 7, the patients will cross over to the treatment for the second period of the sequence they are assigned to. Over the 10-week period, sleep diary will also be completed daily.

10 patients will receive dose-appropriate Melatonin over 8 weeks (Group A), 10 patients will receive 40 sessions of home-based tPCS over 8 weeks (Group D), 10 patients will receive 4 weeks of Melatonin then cross over to receive 4 weeks of 20 sessions of home-based tPCS (Group B) and 10 patients will receive 4 weeks of 20 sessions of home-based tPCS then cross over to receive Melatonin over 4 weeks (Group C).

There will be a washout period of 2 weeks (week 5 and 6) between cross over. Those on a Melatonin group cross over will also go through the same washout period.

3.1 Randomisation and Blinding

Randomisation will be conducted for the patients in a 1:1 ratio to two treatment groups in two sequence periods.

Randomisation will be carried out by one study team member uninvolved in the final data analysis. The study member reporting the actigraphy, and the study member performing data analysis will be blinded.

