3.3 Study Visits and Procedures

Visit to KKH	Visit 1		Visit 2	Visit 3		Visit 4
Timeline	Week 0	Week 1-4	Week 4	Week 6	Week 7-10	Week 10
Procedure	Baseline assessment	First sequence Intervention Period	Post-first sequence assessment	Pre-second sequence assessment	Second sequence Intervention Period	Post-second sequence assessment
Informed Consent ¹	X					
Questionnaires ²	X		X	X		X
Actigraphy ³	X		X	X		X
tPCS ⁴ or Melatonin ⁵		X			X	

¹Informed Consent will be taken at screening visit, i.e. on the same day as when they are identified as a potential participant. Randomisation will be performed after consent taking is completed.

²Sleep questionnaires

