2.1 Sleep disturbance scale for children (SDSC) and Aberrant Behavior Checklist (ABC)

2.2 WHO International Classification of Functioning, Disability and Health, Children & Youth version (ICF-CY) sleep ratings

³Actigraphy. Participants will collect the Actiwatch and wear it for 1 week at home for whole night actigraphic data at start of the sequence period (Week 0 and Week 6) and at the end of the sequence period (Week 4 and Week 10). Patients will return the Actiwatch at the end of the study.

⁴Transcranial Pulsed Current Stimulation (tPCS) – for intervention arm. 45min/ session of tPCS will be performed at home, supervised by a trained personnel, Monday to Friday for 20 sessions over 4 weeks in each sequence period. Participants will be asked to fill out the compliance/ adverse event log daily.

⁵In the control group, participants will be given Melatonin over 4 weeks in each sequence period. They will be asked to fill out the compliance/ adverse event log daily.

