3.3.2 Study Visits and Procedures

Baseline

Prior to commencement of intervention, the patient will undergo:

I. Actigraphy

Actigraphy is a method used to study sleep-wake patterns and circadian rhythms by assessing movement, most commonly of the wrist.^{xxxviii} We will be collecting whole night actigraphic data using Actiwatch (Actiwatch 2, Resironics, USA), worn on the nondominant wrist or ankle – 7 days before intervention commences and in the last week of intervention/control. The four sleep statistics include total sleep time [TST (min)], sleep onset latency [SOL or period of time between bedtime and sleep start (min)], sleep efficiency [percentage of time in bed actually spent sleeping (%)], and wake after sleep onset (WASO) [the time in a sleep interval scored as wake (min)].

II. Sleep disturbance scale for children (SDSC) questionnaire

The SDSC is a 26-item questionnaire that evaluates sleep disturbances including sleep CR initiation/maintenance, breathing, arousal, transitions, daytime sleepiness and sweating in children.^{xxxix}

III. Aberrant Behaviour Checklist (ABC)

The ABC is a behavior rating scale for the assessment of treatment effect. It consists of five factors including (i) Irritability, Agitation, Crying; (ii) Lethargy, Social withdrawal; (iii) Stereotypic behaviour; (iv) Hyperactivity, Non-compliance; and (v) Inappropriate Speech. This will only be used for participants with autistic spectrum disorder.

IV. ICF-CY sleep ratings

Using the WHO International Classification of Functioning, Disability and Health, Children & Youth version (ICF-CY) in the domain of Body Structure/ Function, sleep is evaluated in four aspects: amount of sleep (B1340), onset of sleep (B1341), maintenance of sleep (B1342) and quality of sleep (B1343).¹⁷ Levels of ICF-CY impairment was graded according to frequency, intrusiveness or severity: from 0 (no impairment/ difficulty) to 4 (complete/ constant impairment/ difficulty/ intensity totally disruptive).¹⁸

V. EQ5D

Quality of life measures will be collected and compared between groups.

Intervention

Throughout the intervention period of 6 weeks, patients from the intervention arm will be receiving tPCS, 0.7-1mA for 45 min/ day Monday to Friday (non-public holiday) over 4 weeks in each sequence period. Any adverse event will be recorded in the adverse event log.

Post-intervention

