5.5 Blinding

Blinding is not done to the patients. Only the study member reporting the actigraphy, and the study member performing data analysis will be blinded.

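### Does Section 3.1's two-group 1:1 wording, together with the consent footnote in 3.3, leave the four-sequence allocation or the baseline week unprotected?

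*Protocol*

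**What the plan says.** Section 3.1 gives the allocation rule in one sentence: "Randomisation will be conducted for the patients in a 1:1 ratio to two treatment groups in two sequence periods".

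Section 3 is fuller. On baseline: "At baseline (week 0), all patients will do a one-week sleep actigraphy and complete SDSC questionnaire". On allocation, in the next sentence: "At week 1, patients will be randomised to one of the 4 treatment regimen". It then lists Group A (melatonin in both periods), Group B (melatonin then tPCS), Group C (tPCS then melatonin) and Group D (tPCS in both periods), with 10 children each. At week 7 each child moves to "the treatment for the second period of the sequence they are assigned to". Section 1.2.4 names the design as Balaam's four-sequence design, and Section 8.1 plans 40 children, 10 in each arm.

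In Section 3.3 the table marks consent at Visit 1, week 0. Footnote 1 puts consent on the day a child is identified and adds: "Randomisation will be performed after consent taking is completed". Section 3.3.2 times the actigraphy as "7 days before intervention commences and in the last week of intervention/control". The table shows no visit between week 0 and week 4. Section 5.5 states: "Blinding is not done to the patients".

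**The concern.** The first worry is the allocation rule. Someone building the list from Section 3.1 alone could randomise to two groups, or draw treatment separately in each period. Sequence sizes would then vary by chance, although the design and sample size assume four equal sequences.

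The second worry is timing, and it matters more. Footnote 1 on its own is satisfied by randomising at Visit 1, straight after consent. Visit 1 is the only scheduled contact before treatment, and families are not blinded. They could then know the allocation while the child wears the baseline Actiwatch at home and while they complete the week 0 questionnaires. Blinded reading of the actigraphy would not undo a change in bedtime habits. Week 0 is the one assessment of four that can be kept free of this knowledge, and it is the start value for the first-period start-to-end comparison in Section 8.2.

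**Working it through.** **1. The plan's own figures.** Inputs from Section 8.1: 32 completers (8 per sequence), difference 0.2, within-subject SD 0.15, 20% drop-out.

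- Let d be the period 2 minus period 1 difference within a child. The carryover-adjusted contrast is ½[(d_B − d_A) − (d_C − d_D)].
- Variance = 0.25 × 4 × 2 × 0.15² / 8 = 0.005625, so SE = 0.075.
- Noncentrality = 0.2 / 0.075 = 2.67.
- Noncentral t on 29 df: power 83.1% at one-sided 5% and 73.2% at two-sided 5%. The stated 83% is reproduced with a one-sided test.
- 32 / (1 − 0.20) = 40, which is 4 × 10.

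The sample size therefore already assumes four equal sequences.

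**2. Is Section 3.1 compatible with four groups of 10?**

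| Period | tPCS | Melatonin |
|---|---|---|
| 1 | C + D = 20 | A + B = 20 |
| 2 | B + D = 20 | A + C = 20 |

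It is: the split is 1:1 between two treatments in each of two periods, as Section 3.1 says. A fresh draw at week 7 is not compatible with Section 3, where the second treatment follows from the sequence already assigned.

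**3. The reading that Section 3 excludes, for scale only.** With a separate draw per period, all four sequences would reach exactly 10 with probability about 25% if each period is held at 20/20, and about 0.4% under simple randomisation. With 8 random drop-outs from 40, simulated power is:

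| List | One-sided 5% | Two-sided 5% |
|---|---|---|
| Fixed 10 per sequence | 82.4% | 72.1% |
| 20/20 in each period | 81.4% | 71.0% |
| Unrestricted | 79.2% | 68.3% |

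The loss is about 1 to 3 points one-sided, and up to 4 two-sided.

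**4. Timing, texts side by side.** Section 3 gives a date (week 1) and an order (after the week 0 actigraphy and SDSC). Footnote 1 gives an order only (after consent). Its same-day phrase attaches to consent, not to randomisation. Week 1 satisfies both texts; randomising at Visit 1 satisfies the footnote but breaks Section 3.

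**5. Size if the footnote were nevertheless followed alone (purely hypothetical).** Let b be the week 0 shift between tPCS-first and melatonin-first children caused by knowing the allocation. The protocol gives no value, so b = 0.02, 0.05 and 0.10 are assumed.

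- Bias is b in first-period change and b/2 in change pooled over both periods, because half of each treatment's changes come from period 1.
- Bias is 0 in end-of-treatment values.
- Bias is 0 in the contrast of step 1 if b depends only on the first treatment. C and D then carry the same shift, as do A and B, so it cancels.
- Change SD = 0.15 × √2 = 0.212, assuming SD 0.15 per measured week and independent weeks. The SE is 0.212 × √(2/16) = 0.075 for first-period change (16 v 16) and 0.212 × √(2/32) = 0.053 for pooled changes (32 v 32, treated as independent).

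| b | First-period change | Pooled change |
|---|---|---|
| 0.02 | 5.8% | 5.4% |
| 0.05 | 9.9% | 7.5% |
| 0.10 | 25% | 15% |

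These are false-positive rates at nominal two-sided 5%. The largest needs a shift of half the target effect of 0.20 and a test on first-period change alone.

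**The case for a change.** The strongest case for a change is that ratio, number of sequences and time of randomisation are matters of protocol conduct that cannot be left to a later analysis plan. The section headed randomisation should state them without help from elsewhere. Because no week 1 visit is scheduled, site staff might find it natural to hand over the allocation at Visit 1, and the footnote would not stop them. Baseline protection cannot be restored once lost, and two sentences would secure it.

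Part of this stands. Section 3.1 does not name the four sequences, and footnote 1 is looser than Section 3. But the protocol does state each rule, in its study design section, and nothing in 3.1 or the footnote contradicts it. The absence of a week 1 visit is a matter of logistics: tPCS is given at home by trained personnel, so starting it needs no clinic visit.

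The questionnaires are also less exposed than they first appear. Section 2.3 requires a qualifying pre-intervention sleep score, and Section 11.1 has consent signed once the inclusion criteria are met, so that score precedes consent and hence randomisation. The protocol does not say whether it serves as the week 0 SDSC. The point does not extend to the other questionnaires or to the home actigraphy, so it is only partial reassurance.

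**Conclusion.** No change follows. Read together, the sections give one assignment at week 1, after the week 0 assessments, to four sequences of 10, with the second treatment fixed in advance. Section 3.1 is true shorthand for that scheme, and footnote 1 gives a necessary order without a competing date. Rewording either would restate Section 3 and alter no sample size, sequence size, assessment or result.

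The power loss of about 1 to 3 points one-sided (up to 4 two-sided) applies only to a per-period draw that Section 3 excludes. The false-positive rates apply only if Section 3's week 1 rule is ignored, and they depend on an assumed shift. Even then the bias is zero in end-of-treatment values, and zero in the carryover-adjusted Balaam contrast if the shift depends only on the first treatment. Section 8.2 does not say that its between-treatment t-tests use change from baseline.

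The conclusion assumes that the trial team follows Section 3 as written. Harmonising the wording would be tidy at a future amendment, but the design does not depend on it.

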3.2 Contraception and Pregnancy Testing

Not applicable.

3.3 Study Visits and Procedures

Visit to KKH	Visit 1		Visit 2	Visit 3		Visit 4
Timeline	Week 0	Week 1-4	Week 4	Week 6	Week 7-10	Week 10
Procedure	Baseline assessment	First sequence Intervention Period	Post-first sequence assessment	Pre-second sequence assessment	Second sequence Intervention Period	Post-second sequence assessment
Informed Consent ¹	X					
Questionnaires ²	X		X	X		X
Actigraphy ³	X		X	X		X
tPCS ⁴ or Melatonin ⁵		X			X	

¹Informed Consent will be taken at screening visit, i.e. on the same day as when they are identified as a potential participant. Randomisation will be performed after consent taking is completed.

²Sleep questionnaires

2.1 Sleep disturbance scale for children (SDSC) and Aberrant Behavior Checklist (ABC)

2.2 WHO International Classification of Functioning, Disability and Health, Children & Youth version (ICF-CY) sleep ratings

³Actigraphy. Participants will collect the Actiwatch and wear it for 1 week at home for whole night actigraphic data at start of the sequence period (Week 0 and Week 6) and at the end of the sequence period (Week 4 and Week 10). Patients will return the Actiwatch at the end of the study.

⁴Transcranial Pulsed Current Stimulation (tPCS) – for intervention arm. 45min/ session of tPCS will be performed at home, supervised by a trained personnel, Monday to Friday for 20 sessions over 4 weeks in each sequence period. Participants will be asked to fill out the compliance/ adverse event log daily.

⁵In the control group, participants will be given Melatonin over 4 weeks in each sequence period. They will be asked to fill out the compliance/ adverse event log daily.

3.3.1 Screening Visits and Procedures

All KKH patients who are attending outpatient clinics for neurology service and/ or Physiotherapy and will be screened accordingly to the inclusion and exclusion criteria as stated in the preceding sections 3.2 to 3.4 by the doctors in the clinic. Consent will be taken by anyone from the study team.

3.3.2 Study Visits and Procedures

Baseline

Prior to commencement of intervention, the patient will undergo:

I. Actigraphy

Actigraphy is a method used to study sleep-wake patterns and circadian rhythms by assessing movement, most commonly of the wrist.^{xxxviii} We will be collecting whole night actigraphic data using Actiwatch (Actiwatch 2, Resironics, USA), worn on the nondominant wrist or ankle – 7 days before intervention commences and in the last week of intervention/control. The four sleep statistics include total sleep time [TST (min)], sleep onset latency [SOL or period of time between bedtime and sleep start (min)], sleep efficiency [percentage of time in bed actually spent sleeping (%)], and wake after sleep onset (WASO) [the time in a sleep interval scored as wake (min)].

II. Sleep disturbance scale for children (SDSC) questionnaire

The SDSC is a 26-item questionnaire that evaluates sleep disturbances including sleep CR initiation/maintenance, breathing, arousal, transitions, daytime sleepiness and sweating in children.^{xxxix}

III. Aberrant Behaviour Checklist (ABC)

The ABC is a behavior rating scale for the assessment of treatment effect. It consists of five factors including (i) Irritability, Agitation, Crying; (ii) Lethargy, Social withdrawal; (iii) Stereotypic behaviour; (iv) Hyperactivity, Non-compliance; and (v) Inappropriate Speech. This will only be used for participants with autistic spectrum disorder.

IV. ICF-CY sleep ratings

Using the WHO International Classification of Functioning, Disability and Health, Children & Youth version (ICF-CY) in the domain of Body Structure/ Function, sleep is evaluated in four aspects: amount of sleep (B1340), onset of sleep (B1341), maintenance of sleep (B1342) and quality of sleep (B1343).¹⁷ Levels of ICF-CY impairment was graded according to frequency, intrusiveness or severity: from 0 (no impairment/ difficulty) to 4 (complete/ constant impairment/ difficulty/ intensity totally disruptive).¹⁸

V. EQ5D

Quality of life measures will be collected and compared between groups.

Intervention

Throughout the intervention period of 6 weeks, patients from the intervention arm will be receiving tPCS, 0.7-1mA for 45 min/ day Monday to Friday (non-public holiday) over 4 weeks in each sequence period. Any adverse event will be recorded in the adverse event log.

Post-intervention

Intervention group: Participants will wear the Actiwatch for 7 nights-actigraphic data in the last week of sequence period. Sleep questionnaires will be completed on the last day of the sequence period.

Control group: Participants will take Melatonin daily at bedtime for 4 weeks and wear the Actiwatch for 7 nights-actigraphic data in the last week of each sequence period. Sleep questionnaires will be completed on the last day of the sequence period.

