1.4 Primary Objectives

The primary objective is to assess the effectiveness of tPCS in improving total sleep time by 20% in children with neurodevelopmental disorder, compared with using Melatonin.

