1.5 Secondary Objectives

The secondary objective is to evaluate improvement in other objective sleep measures such as sleep onset latency, sleep efficiency, and wake after sleep onset based on actigraphy; and subjective sleep measures such as sleep initiation, sleep maintenance, sleep quality and change in behaviour based on questionnaires in children with neurodevelopmental disorder.

We also hypothesise that objective improvement in sleep quality will correlate with a decreased score in Sleep Disturbance Scale in Children questionnaire.

1.6 Potential Risks and Benefits:

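### Primary total sleep time moves with time in bed, which this open-label protocol neither steadies in the recording weeks nor lists as an actigraphy statistic

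*Protocol*

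**What the plan says.** Section 1.4 sets the primary objective: "assess the effectiveness of tPCS in improving total sleep time by 20% in children with neurodevelopmental disorder, compared with using Melatonin". Section 3.3.2 lists what is taken from the Actiwatch: "The four sleep statistics include total sleep time [TST (min)], sleep onset latency [SOL or period of time between bedtime and sleep start (min", followed by "sleep efficiency [percentage of time in bed actually spent sleeping" and wake after sleep onset. Time in bed, bedtime and get-up time are not on that list. Section 1.5 makes the remaining three statistics secondary: "other objective sleep measures such as sleep onset latency, sleep efficiency, and wake after sleep onset based on actigraphy".

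Actigraphy is recorded for a week at weeks 0, 4, 6 and 10 (sections 3 and 3.3). On diaries, section 3 says: "Over the 10-week period, sleep diary will also be completed daily". What the diary asks and how it is used are not stated.

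On treatment, "Participants will take Melatonin daily at bedtime for 4 weeks". The tPCS session is 45 minutes at home, Monday to Friday, with no time of day given (section 5.3). Section 5.5 states: "Blinding is not done to the patients"; the person reporting the actigraphy and the analyst are blinded. Section 5.4 places no specific restrictions on participants beyond the exclusion criteria, and section 5.6 lets standard care continue.

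**The concern.** TST is the product of how long the child is in bed and the share of that time spent asleep. Families largely control the first factor. A child put to bed earlier or woken later can gain TST without sleeping any better.

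In an open-label trial the family's knowledge of the treatment can change that behaviour. Only one of the two treatments is tied to bedtime, so there is a plausible way for time in bed to move differently under each. Blinding the actigraphy reporter and the analyst does not help, because what changes is the behaviour and not the reading of it. The distortion could go either way: more time in bed under tPCS would flatter it, and more under Melatonin would hide a benefit.

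**Working it through.** **1. The identity.** Sleep efficiency = TST / time in bed (section 3.3.2), so TST = time in bed × sleep efficiency. At unchanged efficiency, the relative change in TST equals the relative change in time in bed: extra minutes / time in bed.

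**2. The plan's own precision.** Section 8.1 gives 32 evaluable subjects (8 per sequence), a difference of 0.2, a within-subject SD of 0.15 and 83% power at the 5% level. I read 0.2 and 0.15 as 20% and 15% of TST, in line with section 2.1. For Balaam's design:

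- Standard error of the treatment difference = √(2 × 0.15² / 8) = 0.075, with 4 × 8 − 3 = 29 degrees of freedom.
- Power from the noncentral t distribution at 0.2 / 0.075: 83.1% with a one-sided 5% level, 73.2% with a two-sided one. The stated 83% reproduces on the one-sided reading, so both readings are carried below.
- Smallest significant difference: 12.7% one-sided, 15.3% two-sided.

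**3. Size of a time-in-bed shift.** Time in bed is not in the documents. I assume 9-10 hours and add 8 hours to show the range. The shift occurs under one treatment only, efficiency is unchanged, and there is no true effect. The false-positive rate is the noncentral t probability at (relative shift) / 0.075 with 29 degrees of freedom.

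| Assumed time in bed | Extra time | Gain in TST | Share of the 20% target | False positives, two-sided | False positives, one-sided |
|---|---|---|---|---|---|
| 480 min | 30 min | 30/480 = 6.3% | 31% | 13% | 20% |
| 540 min | 30 min | 30/540 = 5.6% | 28% | 11% | 18% |
| 600 min | 30 min | 30/600 = 5.0% | 25% | 10% | 16% |
| 480 min | 60 min | 60/480 = 12.5% | 63% | 36% | 49% |
| 540 min | 60 min | 60/540 = 11.1% | 56% | 30% | 42% |
| 600 min | 60 min | 60/600 = 10.0% | 50% | 25% | 37% |

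The nominal false-positive rate is 5% in each case.

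**4. What bedtimes alone would have to do.** For the observed difference to sit just at significance, extra time in bed under one treatment must be 12.7% of 480-600 min, about 61-76 min (one-sided), or 15.3%, about 74-92 min (two-sided). The full 20% needs 0.2 × 480 = 96 min to 0.2 × 600 = 120 min.

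**5. Equal shifts.** If time in bed moves by the same proportion under both treatments, it cancels in the tPCS-Melatonin contrast. It does not cancel in the comparisons of start with end of treatment, or in the within-group repeated-measures tests, both planned in section 8.2. There the whole 5.0-5.6% (30 min at 9-10 hours) remains.

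**The case against.** **The plan already contains a check.** This is largely right. A reader might infer that nothing in the plan bears on time in bed, or that sleep efficiency cannot reveal its share. The documents do not support either. On the log scale, log TST = log time in bed + log sleep efficiency, so the TST contrast minus the efficiency contrast is the time-in-bed contrast, and time in bed is recoverable as TST / efficiency. A gain made only by bedtimes would show as higher TST with flat or falling efficiency. Sleep onset latency and wake after sleep onset are also planned, and a daily diary is kept. What remains is that the check is indirect, and that the protocol does not list the quantity itself.

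**No unequal shift is shown.** Also right. That Melatonin is taken at bedtime while tPCS has no stated time makes a difference possible. It does not establish one, or its direction.

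**Constant efficiency is an upper bound.** Extra time in bed may not be slept at the previous rate. A reader might infer that a positive TST result could be wholly a bedtime effect. A 30-minute shift supplies only about a quarter to a third of the target, and 96-120 minutes would be needed for all of it, so that inference is not supported.

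**Time in bed can be part of the benefit.** A child who stops waking early stays in bed longer and truly sleeps more. It is therefore tempting, but unwise, to require that benefit be claimed only for the part of TST that time in bed does not explain. Such a rule would discard real gains in sleep maintenance, which section 1.5 counts as an objective.

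**A statistical analysis plan may add the analysis.** It may, and its absence here is no fault. An instruction to families, however, is a study procedure and belongs in the protocol.

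**Conclusion.** The point holds in a limited form. By the protocol's own definitions the primary endpoint depends on time in bed. In a trial where families are not blinded, bedtimes are not steadied in the recording weeks and time in bed is not a listed statistic. A bedtime change that differs between tPCS and Melatonin could be read as a treatment effect; nothing shows that it will be.

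The size is moderate. On the 9-10 hour assumption, 30 minutes under one treatment gives at most 5.0-5.6% and roughly doubles the two-sided false-positive rate, to 10-11%. Sixty minutes gives at most 10-11% and raises it to 25-30%. These figures rest on the assumed time in bed, unchanged efficiency, a shift under one treatment only, and the precision assumed in section 8.1. TST can remain the primary endpoint. The change is worth making because it costs almost nothing and protects the main comparison.

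**What to change.** In section 3.3.2:

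1. Ask families to keep their usual bedtime routine in the four recording weeks (0, 4, 6 and 10). The instruction should concern what the family decides, such as when the child is put to bed or woken, and leave spontaneous waking alone.
2. Add time in bed to the listed actigraphy statistics. It is already needed to compute sleep efficiency, so no new data are collected.
3. Report time in bed by treatment, with the same tPCS-Melatonin contrast as TST, beside TST and sleep efficiency. Label it supportive, with no rule that subtracts it from the primary result.

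The cost is one line of instruction and one extra supportive analysis. If time in bed does differ between treatments, a positive TST result may need more cautious wording.
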